3.0 Investigational Plan

3.1 Study Design

- This is a prospective study performed over a 45-month period. The principal design plan will follow Figure 3 below.
- The study design is based on HCV prevalence order, which was determined based on statistical data from the Arizona Department of Health Services and rate of Hepatitis C per 100,000 (Figure 4). High prevalence counties (123+ cases per 100,000) including La Paz, Mohave, and Yavapai with a total targeted population of 391,999 individuals. Medium-prevalence Counties (101-123 cases per 100,000) are Coconino, Gila, Greenlee, Maricopa, Pima and Pinal with total targeted population of 4,724,421. Low-prevalence counties (<101 per 100,000) including Apache, Cochise, Graham, Navajo, Santa Cruz, and Yuma with a population of 490,388.

- For the initial 9 months the study will utilize direct communication methods (email and text messages) to reach high prevalence areas (Month 1-6), medium prevalence areas (Months 7- 12), and low prevalence areas (Month 13-18).
- The second phase of the study will utilize indirect communication methods (Newspapers and Radio advertisements) and similarly target areas of high prevalence (Month 12-24), medium prevalence (Month 25-30) and low prevalence (Month 31-36).
- The third and last phase is detected for shelter visits and homeless education in high prevalence areas (Month 37-39), mid-prevalence areas (Month 40-42) and low prevalence areas (Month 43- 45).
- This program will follow a streamline cascade of care with three complementary, consecutive portions: Patient education during intervention periods, connection to appropriate care and treatment during gap periods (Figure 3).
- The person responsible for conducting and implementing the project will be the program coordinator. The coordinator will be responsible for responding to calls or emails regarding the study in reference to the FAQ in Appendix 8.3. One hour daily, 5 days per week will be dedicated to answering emails and responding to voice messages or calls. The number of hours will be adjusted according to project performance and needs.

Phase 1: Direct Communication

1. Direct Customized Email Messages

Email messages are customizable and tailored to individual people. The expected response rate as compared to similar healthcare content is about 2%, 112,136 of our targeted group.

a. Generating Email List

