Email listings of Arizona residents will be obtained from National Data Group and mass emails will be sent through sendgrid.com.

b. Frequency and Resources

Emails will be sent out daily during intervention periods of 2 months followed by a 1month gap for two rounds for each of the different prevalence groups. A project coordinator at the Liver Institute PLLC will assure expectations and targeted numbers are met.

c. Email Content

The email content will follow the template in Appendix 8.1, including an introduction of the program coordinator, introduction to the project as well as brief background information on

the disease and its risk factors (Appendix 8.6). It will also include the steps that need to be taken and contact information to answer any questions.

d. Progress Monitoring

Updates will be obtained from the carrier company as documented proof of the number of emails sent. Information will also be collected on how many emails were rejected and how many were opened. This information will then be used to guide adjustments of upcoming steps if expected response rates are not reached.

2. Direct Text Messages

Response rates to text messages are similar to that of emails at about 2% or 112,136 of the targeted population.

a. Generating Phone List

A list of Arizona residents phone numbers will be generated by National Data Group and messages will be sent to the targeted population through Verizon wireless.

b. Frequency and Resources

Text messaging will similarly follow the protocol described in Figure 3. Messages will be sent daily during the intervention period for 2-month followed by a 1-month gap for two rounds for each of the different prevalence groups.

c. Text Content

The text content will follow the template in Appendix 8.2. The message will be brief in comparison to the email content. It will include an introduction of the program coordinator, introduction to the project, the steps that need to be taken to get screened and a link to more information and background on the disease. It will additionally include contact information to answer any questions or connect to screening and treatment resources.

d. Progress Monitoring

Updates will be obtained from the carrier companies as to how many messages were sent daily and how many were rejected. This information will then be used to guide further changes or alterations if expected response rates are not reached.

Phase 2: Indirect Communication

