5.0 Data Management and Analysis

- 5.1 Data Entry and Management
 - >Data will be entered into the electronic data capture system utilized by the Liver Institute PLLC.
 - >Data and results will be entered within a week after they are collected during the mid-study and end-of-study data collection phases.
 - >Data will be de-identified prior to analysis
- 5.2 Data Analysis
 - > A statistician will overlook and conduct final data analysis
 - > Data will be analyzed for trends at the end of the study
 - > Analysis will be completed using IBM SPSS statistics version 24
- 5.3 Results
 - Assuming similar response as obtained for breast cancer or cervical cancer projects, we expect 4% of the targeted population to respond.
 - Based on the prior data, we computed the trend of increase in number of new HCV patients added per year to the pool of diagnosed cohort.
 - According to mapping hep C¹¹, the total number of Antibody screening tests performed in 2016 is 53,580, or 4,465 per month, which is expected to be like current rates of 2019.
 - > We estimate that similar number of subjects will come for self-screening
 - We expected to, at minimum, double the number of screenings to 8,930 tests per month, which will be evaluated after each intervention period as defined in Figure 3. This increase will correlate with the increase in diagnosis rates per 100,000 from 776 to at least 1,552. These numbers will be used as measures of success for the project.
 - Assuming the current rate of 5.2% positive HCV tests holds, we expect at least 464 people to be HCV+ per month from the 8,930 people screened.
 - ➢ From the total number of HCV positive individuals, only 26.1% in Arizona get treatment, which correlates with 120 people per month from the screened population or total of 1440 by the end of the study. Considering there are multiple challenges to treatment and complete eradication, the goal of the study is to promote treatment for those with access to healthcare; expecting to increase treatment rate to about 30%.
 - Statistical data and trends of HCV prevalence over previous years, obtained from the Arizona Department of Public Health, will be compared with the study outcomes to assess the success rate of the study. we expect the number of screened individuals to double and the diagnosis rate to remain at 5.2%. A measure of success is therefore defined as 8,930 or more screening tests performed per month.

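### The 8,930 tests-a-month measure is one statewide figure evaluated after every intervention period, but Phase 1 reaches one county tier at a time, so period results depend largely on tier size

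*Protocol*

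**What the plan says.** Protocol section 2.2 lists patients screened as a primary endpoint. Section 5.3 takes 53,580 antibody tests in 2016, or 4,465 a month, and expects at minimum to "double the number of screenings to 8,930 tests per month, which will be evaluated after each intervention period as defined in Figure 3". It then fixes the criterion: "A measure of success is therefore defined as 8,930 or more screening tests performed per month". The same section states "we expect 4% of the targeted population to respond".

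Section 3.1 divides the counties by prevalence, starting with "High prevalence counties (123+ cases per 100,000) including La Paz, Mohave, and Yavapai with a total targeted population of 391,999 individuals"; the medium tier has 4,724,421 people and the low tier 490,388. Phase 1 uses email and text "to reach high prevalence areas (Month 1-6), medium prevalence areas (Months 7- 12), and low prevalence areas (Month 13-18").

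Under Phase 1, "Emails will be sent out daily during intervention periods of 2 months followed by a 1month gap for two rounds" in each prevalence group, and text messages follow the same pattern. The expected response is about 2% for email and about 2% for text ("The expected response rate as compared to similar healthcare content is about 2%, 112,136 of our targeted group"; "Response rates to text messages are similar to that of emails at about 2% or 112,136 of the targeted population"). The synopsis (Methods) gives a different rhythm: one active month followed by a two-month gap.

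The text gives no tier-specific baseline, no tier-specific target and no per-head version of 8,930.

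**The concern.** The threshold refers to the whole state, while the outreach evaluated in each Phase 1 period refers to 7%, 84% or 9% of the targeted population. The same success per head can therefore miss 8,930 in a small tier and clear it several times over in the medium tier. The smallest tier comes first, so the first evaluation could look like a failure even if outreach works as planned.

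The measure can also disagree with the plan's own Phase 1 monitoring, which asks whether expected response rates, a percentage, are being reached. At stake is how progress on a primary endpoint is read during the study.

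**Working it through.** **Inputs.** Baseline 53,580 a year and the 4% response (section 5.3); tier populations (section 3.1); total targeted population 5,606,808, said to be 80% of the state (section 3.2).

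**The plan's own figures.** 53,580 / 12 = 4,465 and 2 × 4,465 = 8,930, both exact. The tiers sum to 391,999 + 4,724,421 + 490,388 = 5,606,808, also exact.

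**Is the count statewide?** Section 5.3 does not say so. It ties the doubling to a rise from 776 to 1,552 per 100,000. 53,580 / 776 × 100,000 = 6.90 million people, close to the state population implied by section 3.2, 5,606,808 / 0.80 = 7.01 million. The count fits the whole state.

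**Response needed.** Extra monthly response = 4,465 / N. If only outreach tests count towards 8,930, it is 8,930 / N.

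| | High | Medium | Low |
|---|---|---|---|
| N | 391,999 | 4,724,421 | 490,388 |
| Share of total | 7.0% | 84.3% | 8.7% |
| 4,465 / N, per month | 1.14% | 0.095% | 0.91% |
| 8,930 / N, per month | 2.28% | 0.19% | 1.82% |

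The medium-to-high ratio is 4,724,421 / 391,999 = 12.05. It depends on neither the evaluation window nor the split of the baseline between tiers.

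**Example at 4%.** Monthly total = 4,465 + 0.04 × N / w, with the response spread evenly over w months (an assumption, since the plan gives no spread).

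| w | High | Medium | Low | Reaches 8,930 |
|---|---|---|---|---|
| 6 | 7,078 | 35,961 | 7,734 | medium only |
| 4 | 8,385 | 51,709 | 9,369 | medium and low |
| 3 | 9,692 | 67,457 | 11,004 | all |

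**Doubling in the active tier only.** If testing per head is equal across tiers (an assumption), the baselines are 4,465 × share = 312 / 3,762 / 391 a month. Doubling one tier gives a state total of 4,465 + 312 = 4,777, 4,465 + 3,762 = 8,227 or 4,465 + 391 = 4,856. All fall short of 8,930.

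**Passing both rounds of a tier.** Extra tests needed = 2 rounds × window in months × 4,465. A 4% response yields 0.04 × 391,999 = 15,680 (high) and 0.04 × 490,388 = 19,616 (low) in total.

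| Window per round | Extra tests, two rounds | Share of high tier's 4% | Share of low tier's 4% |
|---|---|---|---|
| 1 month | 8,930 | 57% | 46% |
| 2 months | 17,860 | 114% | 91% |
| 3 months | 26,790 | 171% | 137% |

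A one-month window fits the synopsis's active month or section 3.1's gap. Two months fits section 3.1's active months or the synopsis's gap. Three months is a whole round under either.

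**The case against.** The strongest reply is that 8,930 is a project measure. Section 5.3 calls these numbers measures of success for the project, section 5.2 places the analysis of trends at the end of the study, and no action in section 5.3 follows from missing 8,930 in a period. The Phase 1 adjustments hang on response rates, and the comparison planned in the synopsis is between communication methods, not tiers. This stands as a limit on the consequence: no formal tier-level pass/fail decision is written down. It does not remove the problem, because section 5.3 itself says the figure is evaluated after each intervention period.

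A reader might infer that, at 4%, the high tier cannot meet 8,930 in both of its rounds, and that the low tier can do so only with a nearly even split. The documents do not support that as a general statement. It assumes a two-month window and one 4% response shared across both rounds. The plan defines the window through Figure 3, which is not visible in the copy reviewed, and its text conflicts on period length. The synopsis assesses effectiveness in the gap, and the newspaper and shelter monitoring also looks to gap-period screening. With a one-month window the high tier needs only 57% of its 4%. Nor does section 5.3 say that the 4% applies per tier, to Phase 1 alone, or once across both rounds. If the full 4% fell within each three-month round, all three tiers would pass.

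A reader might also want 4% of each tier as the new success bar. That would change the goal: over a six-month block, doubling the statewide count needs 6 × 4,465 = 26,790 extra tests, and 4% gives 15,680 / 188,977 / 19,616, or 59% / 705% / 73% of that.

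**Conclusion.** The point holds as a mismatch between the measure and the unit being evaluated. Followed as written, section 5.3 asks for a 12-fold higher monthly response in the high tier than in the medium tier, and any equal monthly response between 0.095% and 0.91% passes the medium tier alone. Tier size dominates the period result without fixing it in every scenario.

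The 12-fold ratio rests only on the stated populations and an undivided threshold. The monthly totals at 4% assume an even spread and that all tests count, with the background unchanged at 4,465. The single-tier doubling figures assume equal testing per head. Whether a small tier can pass both rounds stays open until the window is defined. The arithmetic behind 8,930 is correct, and the figure remains usable for the state as a whole.

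**What to change.** In section 5.3:

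1. Keep 8,930 a month only as a statewide project-level measure. State that it counts all antibody tests, on the same basis as the 53,580.
2. For the Phase 1 period evaluations, use twice the active tier's own pre-study monthly count, taken from the same source before and during the study. With equal testing per head (an assumption) this would be about 624 / 7,525 / 781 a month, which sums to 8,930.
3. If county counts cannot be obtained, report code-redeemed tests as a percentage of the tier's targeted population, assigned by county of residence, beside the expected 2% per method. Label this a descriptive progress measure, not a success bar.
4. Apply the same scaling to the Phase 3 visits, which also run tier by tier, but not to Phase 2, where the newspaper serves every county and the video advertisement is limited only to the state.
5. Reconcile the period length between the synopsis and section 3.1, and state the evaluation window in the text.

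**Cost.** Protocol wording and possibly one county-level data request; no extra subjects or procedures. Codes are already method-specific and the laboratory already records contact information (section 3.4). The synopsis lets codes be used some months after receipt, so late tests must be credited by county of residence, and a tier's final figure waits until its window closes.

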3.2 Subjects

The targeted study population consists of the entire Arizona population 15+ years of age. According to the ADHS 2017 vital statistics, this age range makes up 80% of the population and a total of 5,606,808 people. The targeted population is divided and ordered as below based on two parameters: known hepatitis C prevalence rates and risk, and the optimal method of communication.

1. Adults (45+)

Baby boomers are 5 times more likely to have hepatitis C than adults from any other age group⁴. According to AZ DHS population statistics, this group makes up 51% of the targeted population; 2,864,689 people. We hypothesize that older people are not exposed to social media as adolescents and young adults are. Therefore, it is important to utilize Email, direct text messages and newspaper outreach to reach this population.

2. Nasal and Injection Drug Users

Another extremely high-risk subgroup is nasal and injection drug users. Figure 5 below shows the rate of HCV positive antibody tests compared to the percentage tested categorized by risk factors. The results indicate 88% of the HCV positive clients had history of nasal drug use compared to 69% amongst all clients¹. We believe reaching out to this community would be an essential step in diminishing hepatitis C. To reach out to this group we plan on distributing pamphlets to treatment and rehabilitation entities.

3. Homeless

Another high-risk subgroup likely to develop infectious diseases is the homeless. According to Phoenix Rescue Mission, there are over 36,000 homeless people in Arizona, 71% of which are in Maricopa county⁸. In addition to their lack of awareness, this group likely do not have access to healthcare or healthy living environments, making them even more prone to fatal viruses and diseases. The most appropriate method to reach this subgroup would be through homeless shelter visits.

4. Adults (20-44)

This age groups makes up about 40% of the targeted population; 2,273,230 people. This group is likely exposed to social media as well as newspapers and direct communication methods such as email and text messages.

5. Millennials / Adolescents (<19 years of age)

We believe this age group, consisting of 8% of the targeted population; 468,889 people, would be equally responsive to social media and directed Emails and text messages. With the growing impact social media has on this category, it has more potential of engaging them than any other means of communication would.

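### The diagnosis-rate target of 776 to 1,552 per 100,000 in section 5.3 does not follow from the section's own test volume and 5.2% positivity, and would be missed even if testing went exactly to plan

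*Protocol*

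**What the plan says.** Protocol section 5.3 takes 53,580 antibody tests in 2016 (4,465 a month) as the baseline and expects at least a doubling to 8,930 a month. On diagnosis it states: "This increase will correlate with the increase in diagnosis rates per 100,000 from 776 to at least 1,552". The next sentence gives the figures their status: "These numbers will be used as measures of success for the project". No denominator or period is given for 776 or 1,552.

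The same section applies a 5.2% positivity to the target volume: "we expect at least 464 people to be HCV+ per month from the 8,930 people screened". Its last bullet uses the term diagnosis rate a second time: "we expect the number of screened individuals to double and the diagnosis rate to remain at 5.2" percent. It then closes with: "A measure of success is therefore defined as 8,930 or more screening tests performed per month".

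The population and duration are stated elsewhere. Section 3.2 says of those aged 15 and over that "this age range makes up 80% of the population and a total of 5,606,808 people", and section 3.1 says: "This is a prospective study performed over a 45-month period". Section 2.2 lists the rate of HCV-positive diagnoses as a secondary endpoint.

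**The concern.** A target that doubles in step with testing, at constant positivity, should equal tests times positivity divided by population. The 776 and 1,552 are far too large for that. If they are used as written, the diagnosis measure fails even when test volume and positivity are exactly as planned, so it cannot separate a working campaign from a failing one.

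The wording adds a second problem. In one section the diagnosis rate is both a rate per 100,000 that doubles and a proportion of tests that stays at 5.2%. Whoever reports the secondary endpoint cannot tell which quantity is meant.

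**Working it through.** **Inputs.** Baseline tests 53,580 a year, target 8,930 a month, positivity 5.2% (section 5.3). Population aged 15+ is 5,606,808, stated as 80% of the total (section 3.2), so the total is 5,606,808 / 0.80 = 7,008,510. Duration 45 months (section 3.1).

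**What reproduces.** 53,580 / 12 = 4,465; 2 × 4,465 = 8,930; 8,930 × 0.052 = 464.4 positives a month; 2 × 776 = 1,552. The section's test and case counts agree with one another. Only the rate per 100,000 does not.

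**Annual reading.** Rate = tests per year × 0.052 / population × 100,000.

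| | Positives per year | Per 100,000 aged 15+ | Per 100,000 total | Stated |
|---|---|---|---|---|
| Baseline | 53,580 × 0.052 = 2,786 | 49.7 | 39.8 | 776 |
| Target | 107,160 × 0.052 = 5,572 | 99.4 | 79.5 | 1,552 |

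The stated target exceeds the planned yield by 1,552 / 99.4 = 15.6 times (aged 15+) or 1,552 / 79.5 = 19.5 times (total). Put the other way, 1,552 per 100,000 aged 15+ is 87,018 diagnoses a year, which would need 87,018 / 107,160 = 81% positivity. On the total population it is 108,772 diagnoses, more than the 107,160 tests.

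**Cumulative reading.** Take 776 as a pool already diagnosed and add every positive over 45 months at target volume: 8,930 × 45 × 0.052 = 20,896, or 372.7 per 100,000 aged 15+ (298.2 total).

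- 776 + 372.7 = 1,149 (aged 15+); 776 + 298.2 = 1,074 (total).
- Ratio to target: 1,552 / 1,149 = 1.35; 1,552 / 1,074 = 1.44.
- Months needed to add 776 per 100,000: 43,509 / 464.36 = 93.7 (aged 15+); 54,386 / 464.36 = 117.1 (total), against 45 available.

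This reading is generous. Half of those positives would be found at baseline volume anyway. Counting only the extra half gives 962 (925).

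**Reading as a testing rate.** 53,580 / 7,008,510 = 764.5 and 107,160 / 7,008,510 = 1,529.0 tests per 100,000 total population per year. 776 / 764.5 = 1.015, so the stated figures agree within 1.5%. On the 15+ denominator the baseline would be 956, which does not fit.

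**The case against.** The strongest reply is that the figures do make sense as annual antibody tests per 100,000 total population. On that reading the defect is one wrong word, and the line merely restates the 8,930 target. That is probably what happened, but the protocol does not say so. The text calls the figures diagnosis rates and makes them measures of success. The match confirms that they are not diagnosis rates.

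Second, 8,930 tests and 464 positives are stated as minimums, so 20,896 is not a ceiling. This is right: the cumulative shortfall holds at target volume. To close it in 45 months, volume would have to be 93.7 / 45 = 2.1 times the target (aged 15+) or 117.1 / 45 = 2.6 times (total). The annual gap is too large for this point to matter.

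Third, section 5.3 gives no denominator, and evaluation follows a figure that is not shown. Crediting all 8,930 monthly tests to the 391,999 people in the high-prevalence counties for 15 months would give 1,777 per 100,000. The protocol describes no such calculation, so it does not rescue the target. The conclusion is limited to statewide denominators.

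Fourth, the closing definition of success rests on tests alone, and the secondary endpoint in section 2.2 carries no threshold. Both points stand and limit the consequence.

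Last, the constant 5.2% is evidently positivity, because an earlier bullet calls it the share of positive tests. That half of the wording problem is editorial.

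**Conclusion.** The figure is wrong as written. As a statewide diagnosis rate, 776 to 1,552 per 100,000 does not follow from section 5.3's tests and positivity on an annual or a cumulative reading, with either population denominator. The annual target is 15.6 to 19.5 times the planned yield. The cumulative target is 1.35 to 1.44 times what is reached at 45 months.

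This assumes testing at exactly 8,930 a month, 5.2% positivity throughout, and one diagnosis for each positive test. The last assumption favours the plan. Section 3.4 confirms antibody results by PCR, and section 5.3 does not say whether 5.2% is before or after confirmation. If it is before, or if some of the counted tests are repeats, confirmed diagnoses are fewer and the gap is wider. Section 4.2 lets each subject enrol only once, which limits repeats among study subjects.

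The defect makes one listed success measure unusable. It does not make the project fail by definition. It should be fixed before any result is compared with it.

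**What to change.** Check the source of 776 first. Then do one of the following:

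- **Relabel.** If the source confirms a testing rate, call 776 and 1,552 annual antibody tests per 100,000 total population and remove them as a measure of diagnosis. They then only repeat the 8,930 target.
- **Restate.** If a diagnosis target is wanted, derive it from the stated inputs: about 50 rising to 99 antibody-positive per 100,000 aged 15+ a year, or 40 to 80 per 100,000 total population. State the denominator, the period, and whether positives are antibody-positive or PCR-confirmed.

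Before fixing a number under the second option, reconcile it with the county tiers in section 3.1. With zero cases in the low tier, they imply at least (123 × 391,999 + 101 × 4,724,421) / 5,606,808 = 93.7 per 100,000, above the derived baseline of 40 to 50. This is only a caution: those rates cover 2002 to 2008, their denominator is not given, and the weighting by the targeted populations is approximate. The finding does not depend on it.

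In either case use positivity for the 5.2%, so that diagnosis rate has one meaning. The cost is a source check and one or two corrected sentences in section 5.3, with no change to conduct.

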1.2 Scientific Rational: Eradication of HCV in Arizona

HCV related malignancies are among the leading causes of mortality in comparison to death from all other causes in Arizona, especially in the middle-age population (Figure 1). The World Health Organization (WHO) set several recommendations with the goal of eradicating HCV by 2030 and several developed countries have taken the initiative to meet these goals¹⁷. The United States on the other hand is significantly lagging to achieve this target. With the current rate of screening, diagnosis, and treatment, it will take several decades to meet the goals of eradication. There is an urgent need to take aggressive action.

LI-HEPC-AZ V1.0 CONFIDENTIAL According to the Institute of Medicine (IOM), 75-90% of HCV positive individuals in the United are unaware of their infection¹⁰. Current HCV standards encourage screening to only those who are thought to be at risk including injection-drug users, baby boomers, persons with known HCV exposure, HIV infection and patients with signs/symptoms of liver disease^{7, 2}. However, these standards leave millions undiagnosed, hence the increasing trends of HCV^{1, 6}. According to the results of the NHANES questionnaire (Figure 2), the primary reason for lack of treatment is lack of diagnosis¹⁶.

For each new acute HCV case that is reported in the United States, the CDC estimates there are approximately 13.9 actual new HCV cases (reported and unreported)¹⁵. This high ratio (total estimated cases to actual reported cases) is primarily a result of the large proportion of individuals with acute HCV who have asymptomatic or minimally symptomatic infection. Therefore, many may continue to transmit the disease to others but find it unnecessary to seek medical care.

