3.4 Population Screening

Screening Promotion

A time limited screening test promotion code, specific to educational outreach methods, will be obtained from Sonora Quest Laboratories and advertised in both direct and indirect communication methods of the educational program. Interested individuals would be required to present a specific promotional code and sign the Informed Consent Form.

Screening Locations

Screening will take place in all branches of Sonora Quest Laboratories over the state of Arizona. Patients will have the opportunity to present at any of the locations and get free screening regardless of their insurance coverage or whether they are considered at risk or not.

Informed Consents

The study, expectations and rights will be explained to patients. Informed consents will be obtained electronically by the screening team to perform anti- HCV test, to share personal information and test result with Liver Institute study investigator team, and to agree to discuss treatment options if HCV test become positive. Consents will be sent to the Liver Institute PLLC where they will be stored in an encrypted electronic data capture system as per Western Institutional Review Board (WIRB) guidelines.

Clinical Parameters

Demographics data and contact information will be recorded for each patient in Sonora Quest Laboratories data system as per their guidelines. Clinical and relevant history pertaining to hepatitis C including diabetes and existing conditions will be collected by study team from HCV positive individuals.

LI-HEPC-AZ V1.0 CONFIDENTIAL ➢ Screening

Screening will be conducted by members of the Sonora Quest Laboratories with ELISA IV antibody test with reflex to HCV PCR test to confirm the diagnosis. Patients will be contacted with their test results by a member of the research team, as well as by Sonora Quest.

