4.2 Exclusion Criteria

- > Patients will only be enrolled once
- > Patients who do not meet the inclusion criteria
- > Patients with a current HCV diagnosis
- > Patients who underwent a liver transplant

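### The monthly minimum of 464 HCV-positive people, and the diagnosis target of 1,552 per 100,000, rest on an unsupported assumption that open-access tests yield the same 5.2% as current risk-driven testing

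*Protocol*

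**What the plan says.** Section 5.3 of the Protocol takes its baseline from 2016: "the total number of Antibody screening tests performed in 2016 is 53,580, or 4,465 per month". It plans at minimum to "double the number of screenings to 8,930 tests per month", and on the source of the extra tests says: "We estimate that similar number of subjects will come for self-screening". It then writes: "Assuming the current rate of 5.2% positive HCV tests holds, we expect at least 464 people to be HCV+ per month". Later in the section positivity is again expected to stay at 5.2%, this time without the condition.

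Two further figures follow from the same step: about 120 people treated a month (26.1% of the positives), and a diagnosis rate rising from 776 to at least 1,552 per 100,000. The latter is named, with the test count, among the measures of success.

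On who is tested now, Section 1.2 says: "Current HCV standards encourage screening to only those who are thought to be at risk". The Synopsis (Research Gaps) adds that primary care tests on abnormal liver results, imaging or disclosed risk behaviour. On who will be tested in the study, Section 3.2 targets all residents aged 15 or over. Section 3.4 lets them "get free screening regardless of their insurance coverage or whether they are considered at risk or not". Section 4.2 excludes "Patients with a current HCV diagnosis".

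**The concern.** The 5.2% is the positivity of tests ordered mostly because someone had a reason to suspect infection. The protocol transfers it unchanged to volunteers who need no such reason, and calls the product a minimum. Section 3.2 itself treats risk as very uneven: "Baby boomers are 5 times more likely to have hepatitis C than adults from any other age group". Opening testing to everyone may therefore change the yield, and no argument is offered that it will not.

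The stake is the reading of the diagnosis result. Doubling the tests doubles the diagnoses only if the yield is constant. A programme that reaches 8,930 tests a month could still miss 1,552 per 100,000 solely because of this assumption. A fall in positivity caused by broader testing could also be misread as a lower HCV burden.

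**Working it through.** **Inputs.** From Section 5.3: 53,580 tests in 2016, a target of 8,930 a month, 5.2% positive, 26.1% treated, 776 and 1,552 per 100,000, and a 4% response. From Section 3.2: a target population of 5,606,808. From Section 3.1: a 45-month study. The yield *p* in the added tests is not in the document and is an assumption throughout.

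**Reproducing the plan's figures.**
- 53,580 / 12 = 4,465 tests a month; 2 × 4,465 = 8,930.
- 8,930 × 0.052 = 464.4, which matches 464.
- 464 × 0.261 = 121, against the stated 120.
- 2 × 776 = 1,552, so the diagnosis target is a straight doubling.

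**Splitting the 464.** About half the tests are existing routine tests, to which the current 5.2% belongs: 4,465 × 0.052 = 232.2. The other 232.2 depends wholly on the added tests. At 8,930 tests:

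positives = 232.2 + 4,465 × *p*

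This reaches 464 only if *p* is at least 5.2%.

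**Sensitivity to the assumed *p*.** The treated column is positives × 0.261. The last column is 776 × positives / 232.2, which further assumes that the diagnosis rate scales with monthly positives; the protocol does not define the 776.

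| Assumed *p* | Positives a month | Change from 464 | Treated a month | Diagnosis rate per 100,000 |
|---|---|---|---|---|
| 1% | 232.2 + 44.7 = 276.8 | −40% | 72 | 925 |
| 3% | 232.2 + 134.0 = 366.1 | −21% | 96 | 1,224 |
| 5.2% | 232.2 + 232.2 = 464.4 | 0 | 121 | 1,552 |

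**Letting volume exceed 8,930.** A 4% response is 0.04 × 5,606,808 = 224,272 people, or 4,984 a month if spread evenly over 45 months. With the existing 4,465 tests, 5.2% throughout gives (4,984 + 4,465) × 0.052 = 491 positives. At that volume 464 needs *p* = (464 − 232.2) / 4,984 = 4.65%.

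**The case against.** The sponsor can fairly say that the sentence is conditional on 5.2% holding, and that its minimum wording also reflects 8,930 being a minimum volume. The first part is true of that sentence, but the condition is dropped when the section later expects 5.2% to continue. The second part stands, but even at the volume implied by a 4% response the added tests must yield 4.65%.

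Some features could raise the yield. Outreach starts in high-prevalence counties, drug users are approached through rehabilitation services, Phase 3 goes to shelters and NA/AA meetings, and people who suspect infection may volunteer. These weaken any claim that 5.2% is an upper limit. They do not secure a floor in every month: the high-prevalence counties hold 391,999 of 5,606,808 people (7%), and Phase 3 occupies only months 37 to 45.

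A reader might infer that 464 is close to a ceiling. The document does not support that, for the reasons of volume and targeting just given. Its own figures on awareness also leave the matter open. If 776 per 100,000 is read as diagnosed prevalence (an assumption), then undiagnosed prevalence among people not diagnosed is about 0.8% with 50% unaware (Section 5.3 puts 50% as diagnosed and aware). With the 75% and 90% unaware of Section 1.2 it is about 2.3% and 7.0%. That range spans 5.2%.

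A reader might also try to derive a yield by giving 5.2% to people aged 45 or over and one fifth of it to everyone else. No section gives 5.2% for that age group, and baby boomers are not the same group as everyone aged 45 or over. Nor can the effect of excluding known HCV be sized, because the protocol does not say whether the 2016 tests included people already diagnosed.

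**Conclusion.** The point holds in a limited form. As written, 464 is a conditional projection presented as a minimum, and the constant 5.2% and the 1,552 target share the same unsupported premise about the added half of the tests. At exactly 8,930 tests, any yield below 5.2% in that half breaks the stated minimum. With 1% to 3% assumed there, the shortfall is 21% to 40%. That range is illustrative and has no source in the document, so it shows sensitivity and is not a better estimate.

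A reader might infer that the whole success definition fails with the yield. It does not: the criterion of 8,930 or more tests a month is independent of 5.2%. Nor is 464 itself the diagnosis benchmark. That benchmark is 1,552 per 100,000, and this is where the assumption could turn a programme that met its screening target into an apparent diagnostic failure.

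**What to change.** In Section 5.3:

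- Delete the words that make 464 a minimum, and the statement that the rate will stay at 5.2%.
- Either give a reason why 5.2% should apply to the added tests, or show a sensitivity range labelled as an assumption. For example, 1%, 3% and 5.2% in the added 4,465 tests give about 277, 366 and 464 positives a month, and about 72, 96 and 121 treated at 26.1%.
- Carry the same range into the 1,552 per 100,000 measure, or make that measure conditional on yield.
- State that positivity of code-redeemed tests will be compared separately with the routine-testing 5.2%. The outreach-specific codes in Section 3.4, and the diagnostic rates by communication method in the Synopsis, already supply the means.

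The cost is a change of wording and a less favourable stated yield. No new data collection is needed.
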